7.2.3.2 MRD analysis reports from HMDS

The following diagnostic categories will be used on HMDS reports to define MRD status:

- B-cell chronic lymphocytic leukaemia (B-cell CLL)
 - Applies to cases with high levels of residual disease: more than 5 x 10⁹/l circulating CLL cells or 30% CLL cells in the BM,
- B-cell CLL – MRD-positive at iwCLL threshold (≥0.01%)
 - Applies to cases with residual disease detectable at or above the iwCLL 0.01% threshold and so not to be considered for treatment cessation.
- B-cell CLL – MRD-negative at iwCLL threshold (<0.01%)
 - Applies to cases eligible for stopping rules, either with no detectable residual disease or with very low levels of detectable disease below 0.01%.
- Other diagnoses, e.g. “see comments” or “inadequate sample”
 - Applies to cases in which the MRD status cannot be determined at the 0.01% threshold. Interpretation of cases with such a diagnosis should be reviewed by the CI and the Clinical Coordinators.

7.2.4 Assessments at disease progression

Patients will be evaluated at disease progression. Disease progression will be defined using the Modified IWCLL Response Criteria (2008) given in Appendix 2.

Progressive disease during or after any period of therapy is characterised by at least one of the following:

- Lymphadenopathy

¹⁵ Defined as months from date of registration to the Extension Study

- An increase in the liver or spleen size by 50% or more and the *de novo* appearance of hepatomegaly or splenomegaly.
- An increase in the number of blood lymphocytes by 50% or more with at least $5 \times 10^9/L$ B lymphocytes (not before at least 12 months of therapy when the lymphocytosis is expected and is treatment related).
- Transformation to a more aggressive histology (e.g., Richter syndrome). Whenever possible this diagnosis should be established by lymph node biopsy.
- Occurrence of cytopenia (neutropenia, anaemia, or thrombocytopenia) attributable to CLL.

The following assessments should be undertaken:

- Samples for central analysis:
 - Peripheral blood 4 x 5mL in EDTA
 - Bone Marrow Aspirate (EDTA)
 - Bone Marrow Trephine Biopsy (directly in formalin)
- Complete physical examination
- Constitutional symptom assessment
- CT-scan Local blood biochemistry and haematology
- Local immunology

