7.2.1 Details of assessments during treatment

Physical examinations:

- Blood pressure
- Pulse
- Temperature
- Weight
- ECOG performance status

A physical examination of the disease should also be included in each clinical assessment, this involves:

- Lymph node disease: the size of the largest lymph nodes in each nodal area (cervical, axillary and inguinal) should be measured in centimetres in 2-dimensions.
- Liver and spleen: If palpable, size of liver and spleen below costal margin should be measured

Constitutional symptom assessment:

- Assessment of B symptoms: fatigue, unintentional weight loss, fevers and night sweats.

Local Laboratory tests:

Haematology

IcICLE

Protocol

- Haemoglobin
- Lymphocyte count
- Neutrophil count
- Platelet count
- Reticulocyte count
- White blood cell count (with differential count)

Biochemistry

- Albumin
- Alkaline Phosphatase (ALP)
- ALT or AST
- Calcium (adjusted)
- Creatinine
- eGFR
- LDH
- Phosphate
- Potassium
- Sodium
- Total Bilirubin
- Total Protein
- Urea
- Urate

Immunology:

- Direct coombs test
- Serum immunoglobulins and electrophoresis
- β_2 microglobulin concentration

CT scans:

- CT scan of the thorax, abdomen and pelvis should be performed to assess lymph node disease

CT scans will be performed locally at IcICLE trial sites and reports may be requested for central review by members of the TMG. Redacted reports (where the patient is identified only by TNO) will be requested by email.

ECG

- 12 lead ECG should be performed to assess patients for signs of atrial fibrillation at Month 1 of treatment.

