APPENDIX 1 – IWCLL RESPONSE CRITERIA (REVISED 2008)

For a complete version of the IWCLL Guidelines for the diagnosis and treatment of chronic lymphocytic leukaemia: a report from the International Workshop on Chronic Lymphocytic Leukaemia updating the National Cancer Institute Working Group 1996 guidelines visit:

<http://bloodjournal.hematologylibrary.org>

Hallek et. al. Blood. 2008 Dec 15;112(13):5259

Definition of response, relapse, and refractory disease

Assessment of response should include a careful physical examination and evaluation of the blood and marrow.

IWCLL Response criteria

Parameter	CR	CRi	PR	SD**	PD
Group A					
Lymphadenopathy	None >1.5 cm	All group A criteria for CR satisfied but reduction in any group B values from CR criteria	Decrease $\geq 50\%$ *		Increase $\geq 50\%$ or appearance of any new lesion, such as enlarged lymph nodes (>1.5 cm), splenomegaly, hepatomegaly, or other organ infiltrates.
Hepatomegaly	None		Decrease $\geq 50\%$		Increase $\geq 50\%$
Splenomegaly	None		Decrease $\geq 50\%$		Increase $\geq 50\%$
Blood lymphocytes	<4000/ μL		Decrease $\geq 50\%$ from baseline		Increase $\geq 50\%$ from baseline – unless treatment-related lymphocytosis
Bone marrow	Normocellular, <30% lymphocytes, no B-lymphoid nodules.		50% reduction in marrow infiltrate, or B-lymphoid nodules		
Group B					
Platelet count	>100 000/ μL		>100 000/ μL or increase $\geq 50\%$ over baseline		Decrease of $\geq 50\%$ from baseline secondary to CLL
Haemoglobin	>11.0 g/dL		>11.0 g/dL or increase $\geq 50\%$ over baseline		Decrease of >2 g/dL from baseline secondary to CLL
Neutrophil count	>1500/ μL		>1500/ μL or >50% improvement over baseline		

Group A criteria define the tumour load, group B criteria define the function of the hematopoietic system (or marrow).

CR (complete remission): all of the criteria have to be met

PR (partial remission) with leucocytosis: at least two of the criteria of group A plus one of the criteria of group B have to be met;

* A decrease in lymph node size by 50% or more either in the sum products of up to 6 lymph nodes, or in the largest diameter of the enlarged lymph node(s) detected prior to therapy. In small lymph nodes (<2 cm), an increase of less than 25% is not considered to be significant.

**SD (Stable disease): is absence of progressive disease (PD) and failure to achieve at least a PR

PD (Progressive disease): at least one of the above criteria of group A or group B has to be met.

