APPENDIX 2 – MODIFIED IWCLL RESPONSE CRITERIA (REVISED 2008)

Due to the mode of action of ibrutinib treatment, a modified IWCLL response criteria will also be used to assess patients where a nodal response has occurred but CR or PR criteria have not yet been obtained.

The modified IWCLL response criteria consist of the following changes to the 2008 IWCLL (Appendix1):

Definition of disease progression for participants receiving Ibrutinib

- Ibrutinib may cause blood lymphocytosis with concomitant reduction in lymphadenopathy and/or splenomegaly.
- In this setting an increase in blood lymphocyte counts, by itself, does not indicate an increased tumour burden, but may rather reflect a re-distribution of leukaemia cells from the lymphoid tissues to the blood. In such cases, increased blood lymphocytosis is not a sign of treatment failure or progressive disease. Such a treatment-related lymphocytosis usually occurs within the first few months of initiating therapy with ibrutinib and can be very marked.
- Treatment-related lymphocytosis, for the purposes of this protocol, is defined as an elevation in blood lymphocyte count of >50% compared to baseline and $>5 \times 10^9/L$

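### Two items in the section 7.2.4 progression list contradict the appendices that define progression: liver/spleen (*and* where either suffices) and late lymphocytosis with continuing response

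*Protocol*

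**What the plan says.** Section 7.2.4 of the protocol opens by naming the governing definition: "Disease progression will be defined using the Modified IWCLL Response Criteria (2008) given in Appendix 2". Appendix 2 is written as a set of changes to Appendix 1, so whatever it does not alter stays as Appendix 1 has it.

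Section 7.2.4 then gives five items of its own, any one of which makes progression. Two matter here:

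- **Liver/spleen.** "An increase in the liver or spleen size by 50% or more and the", and the sentence goes on to require new enlargement of one of these organs.
- **Lymphocytes.** A rise of at least 50% with at least 5 x 10^9/L B lymphocytes, qualified only by "not before at least 12 months of therapy when the lymphocytosis is expected and is treatment related".

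In the progression column of Appendix 1, a 50% increase has its own entry in the hepatomegaly row and again in the splenomegaly row. The lymphadenopathy row adds "or appearance of any new lesion, such as enlarged lymph nodes (>1.5 cm), splenomegaly, hepatomegaly, or other organ infiltrates". The rule for combining them is "at least one of the above criteria of group A or group B has to be met". The blood-lymphocyte row exempts treatment-related lymphocytosis.

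Appendix 2 describes the setting, "Ibrutinib may cause blood lymphocytosis with concomitant reduction in lymphadenopathy and/or splenomegaly", and rules: "In such cases, increased blood lymphocytosis is not a sign of treatment failure or progressive disease".

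The PFS definition cites the 2008 IWCLL criteria in the synopsis and section 2.2, and the modified 2008 criteria in section 12.1.2. Sections 7.1 and 7.11.1 tie stopping ibrutinib for progression to Appendix 2.

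**The concern.** Progression is the main component of the PFS event, and 7.2.4 is the section a site would naturally open when progression is suspected. If its list and the appendices classify the same patient differently, two sites following different pages will record different events. The two departures pull in opposite directions: the liver/spleen item can lose an event, and the lymphocyte item can add one. The net bias therefore cannot be predicted. A site working from the list could also stop ibrutinib, or continue it, when Appendix 2 says otherwise.

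**Working it through.** The plan gives no figure to reproduce. The check is a comparison of the texts, using three patients with assumed values. In each case no other item in the 7.2.4 list is met.

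| Case (assumed values) | 7.2.4 read literally | Appendices |
|---|---|---|
| A. Spleen palpable at baseline, 4 cm, later 7 cm: 7/4 - 1 = +75%; no newly enlarged organ | Not progression | Progression (Appendix 1) |
| B. Spleen not palpable at baseline, later 5 cm: newly enlarged; percentage change undefined (division by 0) | Not progression | Progression (Appendix 1) |
| C. Month 15, lymphocytes from 40 at baseline to 65 x 10^9/L, at least 5 x 10^9/L of them B lymphocytes, nodes still reduced: 65/40 - 1 = +62.5% | Progression | Not progression (Appendix 2) |

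**Cases A and B.** Appendix 2 changes nothing about liver or spleen, so Appendix 1 governs, and there either finding is enough. Section 7.2.1 explains why the conjunction is so restrictive: "If palpable, size of liver and spleen below costal margin should be measured". An organ that becomes palpable for the first time has no earlier clinical size from which to grow 50%. On clinical measurement, then, one organ cannot meet both halves. Taken literally, the item could be met only if one organ grew while the other newly enlarged.

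**Case C.** Appendix 2's only statement on timing is that this lymphocytosis usually appears in the first few months. That describes the usual course and sets no cut-off. A rise at month 15 with nodes still reduced falls inside the Appendix 2 exception and outside the 7.2.4 one.

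**How common case C could be.** Section 7.8.4 gives a median of 18.7 weeks to resolution in CLL. Twelve months is about 52.1 weeks, and 52.1/18.7 = 2.8 medians. Section 1.2.3 says that adding rituximab seems to abrogate the lymphocytosis, so the case should be rarer still in the obinutuzumab extension. The protocol gives no frequency for any of the three cases.

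**Scale of one reclassified patient.** With 20 patients in a cohort and censoring ignored, the shift is 1/20 = 5.0 points. Against the exact (Clopper-Pearson) 95% interval at assumed PFS values:

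| Assumed PFS | 95% interval | Width | 5.0 / width |
|---|---|---|---|
| 14/20 = 70% | 45.7 to 88.1 | 42.4 | 0.12 |
| 16/20 = 80% | 56.3 to 94.3 | 37.9 | 0.13 |
| 18/20 = 90% | 68.3 to 98.8 | 30.5 | 0.16 |

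This would hold for any single misclassification in a cohort of 20. It gives a scale and is not evidence of how often the conflict arises.

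**The case against.** The strongest reply is that the governing definition is already fixed. Section 7.2.4 itself defers to Appendix 2, sections 7.1 and 7.11.1 tie stopping to Appendix 2, and section 12.1.2 ties PFS to the modified criteria. Anyone who follows those references classifies all three cases correctly. The *and* is probably a slip, since one organ can hardly satisfy both halves, and many sites would read it as *or*. This limits the consequence. It does not remove the contradiction, because the list is presented as what characterises progression.

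A reader might infer that the liver/spleen item misses progression generally. It does not. Any one of the five items is enough, so what is lost is progression confined to liver or spleen with no other item met. A reader who takes the bare lymphadenopathy item as shorthand for the whole Appendix 1 row would also catch new organ enlargement (case B), but not growth of an organ already enlarged (case A).

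On lymphocytes, Appendix 2 defines treatment-related lymphocytosis by nearly the same thresholds that 7.2.4 uses for progression. With no time boundary, the Appendix 1 exemption would cover almost every qualifying rise, and the 12-month clause can fairly be read as supplying that boundary. This is a good reason to keep the clause. What remains in conflict is a late rise with continuing nodal or splenic response. Section 7.8.4, which says transient lymphocytosis without other clinical findings should not be called progression, leans the same way as Appendix 2 but does not settle whether a late rise is transient.

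A reader might also cite section 8.1.1, which keeps patients with treatment-related lymphocytosis on treatment, as a further contradiction. It is an adverse-event reporting rule and does not decide whether a rise after 12 months is treatment-related.

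**Conclusion.** The point holds as a minor one: two items in 7.2.4 are wrong as written when set against the appendices that the section names. The liver/spleen item can miss progression confined to those organs at any time on study. The lymphocyte item can add progression only in patients with a late rise and continuing nodal or splenic response, so it bears mainly on 2-year PFS.

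The size cannot be computed from the protocol. It is probably small, on the assumptions that most sites read *and* as *or* and that late lymphocytosis with continuing response is uncommon. Treatment is affected only where sites work from the list instead of Appendix 2. The primary MRD endpoint and the extension's activity decision rule do not use this definition.

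The differing PFS labels might suggest two competing endpoint definitions. The documents do not support giving that much weight, because Appendix 1 already exempts treatment-related lymphocytosis. It is a label correction.

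**What to change.** In section 7.2.4:

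1. Liver/spleen item: change *and* to *or* between the 50% increase and the new enlargement.
2. Lymphocyte item: keep the 12-month clause and add *and not accompanied by continuing reduction in lymphadenopathy or splenomegaly (Appendix 2)*. If the investigators mean 12 months as an absolute limit, write that limit into Appendix 2 instead.

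In the synopsis and section 2.2, cite the modified 2008 IWCLL criteria for PFS, as section 12.1.2 does.

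Do not add a *from baseline* reference to the lymphocyte item as part of this correction. Although it would match Appendix 1, it is a change of substance: it would expressly exclude a rise from the lowest count that stays below baseline, which the present wording leaves open.

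The cost is one word and one clause in 7.2.4 (or one sentence in Appendix 2 in place of the clause), plus one label in each of two places. No new data, CRF item or analysis is needed.

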7.3 Sample Collection

All bone marrow biopsies and aspirate should be sent to the Haematological Malignancy Diagnostic Service (HMDS) for analysis. If additional samples are taken for diagnostic purposes at time points not specified for the IcICLLe study please also send these to HMDS for analysis where possible.

Following informed consent, the following samples will be taken for flow cytometry and histological analysis and sent to the HMDS for analysis.

Samples must be taken and sent on Mondays and Tuesdays only.¹⁶ They should be put in the post before 2 pm on the same day of collection, to arrive at the HMDS within 24 hrs (address in section 7.3.1)

Pre-paid Royal Mail Special Delivery Safeboxes will be supplied to sites to ensure that samples can be tracked and will reach HMDS within 24 hours of the sample being taken.

For example, ibrutinib should be taken on day 0 around 10 am. 4 hours after this administration, bloods will be taken (2 pm) and be put into the post to arrive at the HMDS within 24 hours. All samples sent to the HMDS should be accompanied by a completed sample request form. Sites should retain the original Sample Request Forms in the ISF and send a copy with the samples to HMDS.

It is the responsibility of the trial site to ensure that samples are appropriately labelled in accordance with the trial procedures to conform to the General Data Protection Regulation (GDPR) 2018.

Biological samples collected from patients as part of this study will be transported, stored, accessed and processed in accordance with national legislation relating to the use and storage of human tissue for research purposes and such activities shall at least meet the requirements as set out in the 2004 Human Tissue Act.

Please refer to the sample collection guidelines for more information.

If the patient's ibrutinib/obinutuzumab treatment is held or delayed, please contact the Trials Office in relation to possible changes to timings of sample collections.

¹⁶ Day 2 of treatment may fall on a Wednesday or Thursday (Extension Study patients only); in this circumstance it is permissible to send samples on that day. If there are any issues surrounding sample collection dates please contact the IcICLLe trial office for help and advice.

7.3.2 Sample Collection Tables

Table 2: Initial Phase Cohort (A) and (B)i sample collection:

	Sample time point ID	Peripheral Blood			First-pull bone marrow aspirate		Trepine Biopsy
		4 x 5mL EDTA		2 x 5mL EDTA	0.5 - 2mL EDTA		
		1		3	4		6
2 weeks pre-treatment (screening)	A	X			X		X
Day 1: Pre-treatment	B	X					
Day 1: 4 hours after first dose	C			X			
Day 2: 24 hrs after first dose	D			X			
Week 1	E			X			
Week 2	F			X			
Month 1	G	X			X		X
Month 2	H			X			
Month 6	I	X			X		X
Month 9	J			X			
Month 12	K			X			
6 monthly monitoring	L			X			
6 months after clinical or MRD(-)ve remission	MRD	X			X		X
Disease progression	DP	X			X		X
Any other time - i.e. query on cytopenia	QUE	X			X		X

Table 3: Extension Study Cohort (B)ii and (B)iii sample collection

		Extension Study					
		Peripheral Blood			First-pull bone marrow aspirate		Trepine Biopsy
		4 x 5mL EDTA		2 x 5mL EDTA	0.5 - 2mL EDTA		
Sample time point ID	1		3	4		6	
2 weeks pre-treatment (screening)	A	X			X		X
Day 0: Pre ibrutinib treatment	B	X					
Day 0: 4 hours post ibrutinib treatment	C			X			
Day 1: Pre obinutuzumab treatment	D			X			
Day 2	E			X			
Week 1	F			X			
Week 2	G			X			
Month 1	H	X			X		X
Month 3	I			X			
Month 6	J			X			
Month 9	K	X			X		X
Month 12	L			X			
6 monthly monitoring	M			X			
6 months after clinical or MRD(-)ve remission	MRD	X			X		X
Disease progression	DP	X			X		X
Any other time - i.e. query on cytopenia	QUE	X			X		X

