Participants will be recruited from TAP centres with expertise in the diagnosis and treatment of CLL. It is envisaged that all eligible patients at these centres will be offered the opportunity to participate in the study.

Assessment of response

Assessment of MRD will be carried out on peripheral blood samples throughout the study. It will be measured by flow and assessed using current IWCLL guidelines (refer to Appendix 1 for these guidelines and references). Assessment of MRD in bone marrow will be carried out on monotherapy patients after 6 months of continuous treatment with ibrutinib, and for combination therapy patients at 9 months (3 months after completion of combination therapy to allow for washout of antibodies). This is in line with comparable studies and IWCLL guidelines on assessment of MRD; that is to say that response should be assessed 2 months after the treatment has finished. Whilst extension study patients will continue on ibrutinib monotherapy after the 6 cycles of obinutuzumab, the effect of any synergy between ibrutinib and obinutuzumab should be evaluated after cessation of the second IMP. We can thus determine if administration of the combination therapy leads to a sustained response in patients when examining MRD in both peripheral blood at 1, 3, 6 and 9 months and bone marrow at 1 and 9 months.

Biological response will be assessed by way of peripheral blood and/or bone marrow examinations taken over a 12 month period. Further samples will also be collected every 6 months after this date, and 6 months after the patients achieve a clinical complete or MRD negative remission. If patients become confirmed MRD negative they will also stop treatment.

The key biological end-points will be complete following 6 months of trial treatment with secondary end-points of Modified IWCLL Response Criteria continuing to 12 months and beyond if patients continue to respond.

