7.2 Assessments

Following informed consent, patients will be required in clinic at the times described in the Assessment Schedule (see Section 5.3 for screening and 7.2.2 for treatment)

Please note that for cohort (B)ii only the Day 0 assessment is arranged as below:

- Physical examination and central and local samples should be taken pre-ibrutinib treatment. The first dose should be on either a Monday or Tuesday to allow for sample delivery
- Central samples should be taken four hours post-ibrutinib administration

For all cohorts, on Day 1, (24 hrs post 1st dose), the blood sample should be taken before the patient begins the obinutuzumab infusion.

Every effort should be made to adhere to the protocol scheduled visits. Visits from months 1 onwards should be scheduled as close as possible but may be scheduled within +/- 7 days. HMDS assessments at other points:

- Following detection of MRD negativity, assessment times will change. Please see Section 7.2.3)
- If there is a clinical need for an additional bone marrow examination—e.g. to identify cause of cytopenia—please send the sample to HMDS for analysis (see section 7.3)

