7.2.2 Assessment schedule

Day 0 pre-ibrutinib treatment (cohort (B)ii only)

- Samples for central analysis
 - Peripheral blood sample 4 x 5 mL in EDTA
- Local laboratory tests
- Complete physical examination

Day 0 4 hrs post 1st ibrutinib treatment (cohort (B)ii only)

- Samples for central analysis
 - Peripheral blood 2 x 5mL in EDTA
- Local laboratory tests
- Local immunology

Day 1 (before the 1st obinutuzumab treatment)

- Samples for central analysis:
 - Peripheral blood 2 x 5mL in EDTA
- Complete physical examination
- Local laboratory tests

Day 2

- Samples for central analysis:
 - Peripheral blood 2 x 5mL in EDTA
- Complete physical examination

- Local laboratory tests

Day 8 and Day 15

- Samples for central analysis:
 - Peripheral blood 2 x 5mL in EDTA
- Local laboratory tests

Month 1

- Samples for central analysis (bone marrow samples not required for IcICLLe patients who have transitioned to the Extension Study):
 - Peripheral blood 4 x 5mL in EDTA
 - Bone Marrow Aspirate (EDTA)
 - Bone Marrow Trepine Biopsy (directly in formalin)
- Complete physical examination
- Constitutional symptom assessment
- ECG
- Local laboratory tests
- Disease Response according to modified IWCLL criteria (Appendix 1 & 2)

Month 3

- Samples for central analysis:
 - Peripheral blood 2 x 5mL in EDTA
- Complete physical examination
- Local laboratory tests
- CT scan

Month 6

Cohort (A) and B(i) (IcICLLe):

- Samples for central analysis:
 - Peripheral blood 4 x 5mL in EDTA
 - Bone Marrow Aspirate (EDTA)
 - Bone Marrow Trepine Biopsy (directly in formalin)
- Disease Response according to modified IWCLL criteria (Appendix 1 & 2)

Cohort (B)ii & (B)iii (IcICLLe Extension Study):

- Samples for central analysis
 - Peripheral blood 2 x 5mL in EDTA

All Cohorts

- Complete physical examination
- Constitutional symptom assessment
- Local laboratory
- Local immunology
- CT scan: should only be performed if the result of the 3 month scan was abnormal.

Month 9

Cohort (A) and (B)i (IcICLLe):

- Samples for central analysis:
 - Peripheral blood 2 x 5mL in EDTA

Cohort (B)ii & (B)iii (IcICLLe Extension Study):

- Samples for central analysis:
 - Peripheral blood 4 x 5mL in EDTA
 - Bone Marrow Aspirate (EDTA)
 - Bone Marrow Trepine Biopsy (directly in formalin)
- Disease Response according to modified IWCLL criteria (Appendix 1 & 2)

All Cohorts

- Complete physical examination
- Local laboratory tests

Month 12 and every 6 months thereafter

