7.2.3 MRD negative remission (all patients)**Assessments to confirm MRD negative remission**

All patients will receive treatment on IcICLLe until MRD negativity has been confirmed or until disease progression, whichever is earliest. Confirmation of complete MRD negativity is given by the HMDS once MRD negativity has been recorded for 6 months.

As per IWCLL guidelines, (refer to Appendix 1 for these guidelines and references), MRD negativity should be measured by three consecutive MRD negative peripheral blood (PB) results at 3 month intervals. To confirm the remission 6 months after the first MRD negative PB sample, a bone marrow (BM) examination should be performed with the third blood sample, both PB and BM aspirate should be sent to the HMDS for analysis of the MRD level.

At 6 months following clinical complete remission or the first MRD negative peripheral blood result (as described above), the following assessments should be undertaken to confirm the remission.

- Samples for central analysis:
 - Peripheral blood 4 x 5mL in EDTA
 - Bone Marrow Aspirate (EDTA)
 - Bone Marrow Trepine Biopsy (directly in formalin)
- Complete physical examination
- Constitutional symptom assessment
- CT-scan should be performed to confirm clinical complete MRD negative remission.
- Local blood biochemistry and haematology
- Local Immunology

If the bone marrow does not confirm MRD negativity, the patient should continue to receive ibrutinib/obinutuzumab until disease progression.

Should a patient be confirmed to be in MRD-negative remission by the bone marrow examination, trial treatment will cease according to the MRD negative remission stopping rules (7.2.3.1). At the end of the extended treatment period defined by the stopping rules, we would strongly recommend that a BM sample is sent with a PB sample to HMDS 2-4 weeks prior to the scheduled stopping date for ibrutinib to confirm the level of continued MRD response.

Subsequently, a patient in MRD-negative remission should be monitored by peripheral blood samples taken every 6 months and sent to HMDS for analysis. During this monitoring period an optional BM sample may be requested to confirm PB results.

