APPENDIX 8 – KINETICS SUB-STUDY

[figure not shown]
Patients who fulfil the eligibility criteria for the IcICLLe trial may be asked to participate in an optional kinetic assessment study, which will run alongside the IcICLLe trial and will be based at King's College London.

Study Design

The objective of this study is to investigate tumour kinetics during ibrutinib therapy.

Ibrutinib treatment will start on day 1.

Effect of ibrutinib on the release proliferation and loss rate of CLL cells

Blood sampling intervals ↓

Additional visits over and above the basic IcICLLe study are indicated in red

Assessment Schedule – Kinetic Sub-study

	Day (-) 0	Day 1*	Day 2*	Day 4	Day 8*	Day 15*	Day 29*	Day 57*	Day 61	Day 64	Day 73	Day 85
	Start of cycle 1	Ibrutinib treatment starts					Week 4 Start of cycle 2	Week 8				
Blood samples	X	X					X	X	X	X	X	

*The patient is already required to be in clinic on these days for the IcICLLe trial

Investigations:

On day 1 of each labelling (day (-)0) patients will receive deuterated glucose every 30 minutes for 10 hours. A blood sample will be taken before starting and finger prick samples every 1, 3, 5, 8 and 10 hours and on days 1, 2, 4 and 8 to assess deuterated glucose levels.

EDTA blood samples will be taken at the indicated time points. The day 1 sample will be taken immediately before and 4 hours after idelalisib administration. Peripheral blood mononuclear cells will be purified by density centrifugation and cryopreserved in DMSO as viable cells in minimum aliquots of

2×10^7 . A minimum of 6 aliquots per time point will be stored. A full blood count will also be performed at each time point. Samples will be shipped in batches to Kings College Hospital on dry ice for sorting. Deuterium incorporation into CD19+ and other subsets will be measured in [name] laboratory at St Georges Hospital.

Clinic Attendance:

All blood samples to be collected before study drug administration (day 0 to day 1) should ideally be taken at times where samples are required during the screening process, to limit the inconvenience caused to the patient. For blood samples following drug administration, the patient will only be required to attend clinic on five extra occasions – days 4, 61, 64, 73 and 85.

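### Table 2 puts the initial-phase blood sample H at Month 2, while Schedule A and section 7.2.2 require it at Month 3; Appendix 8 carries a related visit mismatch (minor)

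*Protocol*

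**What the plan says.** Four places in the protocol fix the early blood samples for cohorts (A) and (B)i.

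- **Section 7.3.2**, under "Table 2: Initial Phase Cohort (A) and (B)i sample collection", runs Month 1 (ID G), Month 2 (ID H), Month 6 (ID I), Month 9 (ID J), Month 12 (ID K). Row H is a 2 x 5 mL sample. There is no Month 3 row.
- **Schedule A** has month columns 1, 3, 6, 9 and 12. Its central peripheral blood row is marked in every column, Month 3 included. There is no Month 2 column.
- **Section 7.2.2** has a Month 3 block that asks for central "Peripheral blood 2 x 5mL in EDTA" with no cohort restriction. It has no Month 2 block.
- **Appendix 8** (kinetics sub-study) stars Day 57 (Week 8) under the note "The patient is already required to be in clinic on these days for the IcICLLe trial". It then states that "the patient will only be required to attend clinic on five extra occasions – days 4, 61, 64, 73 and 85".

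Table 3, for the extension cohorts, has Month 3 and no Month 2. The tolerance is in section 7.2: "Visits from months 1 onwards should be scheduled as close as possible but may be scheduled within +/- 7 days".

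On use of the samples, section 3 says "Assessment of MRD will be carried out on peripheral blood samples throughout the study", and section 12.1.2 makes absolute CLL counts in blood a secondary outcome.

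**The concern.** A site that works from Table 2 would send a sample at a time when the main trial has no visit, and would send nothing at Month 3. A site that works from Schedule A or section 7.2.2 would do the opposite. The same time-point ID could then hold samples from two different times on treatment.

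This matters because the protocol wants the dynamics of response from changes in CLL levels in blood and marrow (section 12.1.2). Section 7.8.4 says that lymphocytosis on ibrutinib typically starts in the first weeks and resolves at a median of 18.7 weeks in CLL. Month 2 and Month 3 both fall before that median, so a mixture of the two would blur the blood curve at one of its early points.

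Appendix 8 repeats the Month 2 timing: it relies on a Week 8 main-trial visit that Schedule A does not contain. The list of extra attendances for sub-study participants is therefore wrong as well.

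**Working it through.** The protocol gives no figure to reproduce. The check is a comparison of the schedules plus arithmetic on days.

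**1. Is a row lost from Table 2?** The IDs run G, H, I, J, K without a break for Months 1, 2, 6, 9 and 12. A dropped Month 3 row would leave a gap in the letters. The table really has Month 2 and not Month 3.

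**2. Does the visit window reconcile the two?** Treatment starts on Day 1 and the window is 7 days either side.

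| Month length | Month 2 (latest) | Month 3 (earliest) | Days between |
|---|---|---|---|
| 28 days | Day 1 + 56 = 57 (64) | Day 1 + 84 = 85 (78) | 78 − 64 = 14 |
| Calendar, about 30.4 days | about Day 62 (69) | about Day 92 (85) | 85 − 69 = 16 |

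On either convention no single sample meets both instructions.

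**3. How far apart are the nominal times?** In calendar months, Month 2 is about 8.7 weeks and Month 3 about 13.0 weeks: 13.0 − 8.7 = 4.3 weeks. With 28-day months the difference is exactly 4 weeks. Both precede 18.7 weeks.

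**4. Spacing of scheduled blood samples from Month 1.**

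- Table 2: Months 1, 2, 6, 9, 12; gaps of 1, 4, 3 and 3 months.
- Schedule A and 7.2.2: Months 1, 3, 6, 9, 12; gaps of 2, 3, 3 and 3 months.

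**5. Is Month 6 affected?** Schedule A, section 7.2.2 and Table 2 all place blood, marrow aspirate and trephine at Month 6. The scheduled primary-endpoint sample agrees throughout.

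**6. Appendix 8 attendances.** Day 29 is starred as Week 4, which corresponds to the Month 1 visit. On the same 28-day count Month 2 is Day 57 and Month 3 is Day 85. The extension uses this mapping too: section 7.1.2 gives infusions on Days 29, 57, 85, 113 and 141, and Schedule B shows them at Months 1 to 5. Under Schedule A, then:

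- Day 57 is not a main-trial visit, so it is extra;
- Day 85 is the Month 3 visit, so it is not extra.

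Printed list: 4, 61, 64, 73, 85 (five days). Reconciled list: 4, 57, 61, 64, 73 (five days). The count is unchanged.

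**The case against.** The strongest reply is that this is one table cell. Schedule A and section 7.2.2 both state the Month 3 blood, and 7.2.2 gives the tubes. Section 7.3 also points sites to separate sample collection guidelines, a request form and the trial office. A site may never act on Table 2 alone. That stands, and it keeps the severity low. It does not remove the contradiction, because Table 2 is a live instruction in the protocol and Appendix 8 shares its timing.

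Four stronger readings are tempting and are not supported.

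- **That Month 3 blood is never collected in the initial phase.** Schedule A and section 7.2.2 require it. The fault is inconsistent specification.
- **That the MRD confirmation chain, and so the primary endpoint, is broken.** Section 7.2.3 asks for "three consecutive MRD negative peripheral blood (PB) results at 3 month intervals", and on Table 2 the first scheduled run with that spacing is Months 6-9-12 rather than 3-6-9. But the chain starts from a patient's first negative result, and section 7.2 says assessment times change once negativity is detected. Section 12.2.2 expects negligible MRD negativity on ibrutinib alone, and the monotherapy stopping rules in 7.2.3.1 start from 12-18 months.
- **That a planned comparison with the extension at Month 3 is lost.** Sections 12.3 and 12.4 say that the two phases are analysed separately, and no such comparison is specified.
- **That sub-study participants face six extra visits rather than five.** This counts Day 57 as extra but forgets that Day 85 then becomes a main-trial visit.

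**Conclusion.** The contradiction is real and minor. One of the five blood time points between Months 1 and 12 in the initial phase is specified about 4 weeks apart in different sections, and the visit window leaves 14 to 16 days that no sample can span. Up to 40 planned patients are exposed; how many are affected depends on which section each site followed, which the protocol cannot show. The effect is confined to the early course of CLL and MRD levels in blood.

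The protocol does not say outright which month was meant. Month 3 is the better-supported reading, since Schedule A, section 7.2.2 and the parallel Table 3 agree on it, against Table 2 and the Day 57 star in Appendix 8.

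The unchanged count of five in Appendix 8 assumes 28-day months, as its Day 29 marking suggests. On calendar months Day 85 falls at about the opening edge of the Month 3 window, so the result then depends on booking the two together.

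**What to change.** - In Table 2, change time point H from Month 2 to Month 3, so that it agrees with Schedule A and section 7.2.2. Check the sample collection guidelines and request form for the same entry.
- In the analysis data, place any H samples already taken by their actual collection date and not by the ID.
- In Appendix 8, reconcile the markings with Schedule A: remove the star from Day 57, mark Day 85 as the Month 3 visit, and list the extra days as 4, 57, 61, 64 and 73. Leave the count at five.

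The cost is protocol wording and a note to sites. The main trial needs no additional blood draws.
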